5.1 Investigational product/treatment

This trial is designed to investigate the additional value of Density Spectral Array monitoring, provided by the Narcotrend™ monitor in the “speed of emergence” after general anaesthesia. compare traditional general anaesthesia with sevoflurane using a MAC value and subjective clinical parameters to the objective and continuous approach to depth of hypnosis by DSA monitoring with the primary outcome parameter “speed of emergence”. The investigational product is the validated Narcotrend™ monitor, an electroencephalographic monitor, that is regularly used in anaesthesia practice in the Sophia children’s hospital and will be used according to intended purpose. The extended version as used in the operating room in the Sophia Children’s hospital offers a diversity of diagrams including Density Spectral Array.

The electroencephalographic Narcotrend™ monitor records frontal EEG-activity. Standard paediatric ECG electrodes are used for EEG registration.

5.2 Use of co-intervention (if applicable)

Not applicable.

5.3 Escape medication (if applicable)

The investigator can use every medication that is needed for good clinical practice. Each opioid or anaesthetic that is used outside the protocol will be considered as escape medication. The subject will be secondary excluded from analysis when escape medication is used.

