1.3 General anaesthesia supplemented with caudal analgesia

According to standard care, at Erasmus MC Sophia Children’s Hospital many surgical procedures are performed under general anaesthesia supplement with caudal analgesia. To exclude the impact of opioids on speed of recovery, we choose to include patients undergoing a surgical procedure requiring general anaesthesia supplemented with caudal analgesia.

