4.3 Exclusion criteria

A potential subject who meets any of the following criteria will be excluded from participation in this study:

4.3.1 primary exclusion criteria

- Withdrawal of informed consent
- (Chronic) use of drugs influencing the electroencephalogram
- Use of premedication
- Known intolerance for sevoflurane
- Parents/legal guardians unable to communicate in Dutch

4.3.2 secondary exclusion criteria

- protocol violation
- data registration failure

[figure not shown]

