8.4.1 Specific criteria for withdrawal (if applicable)

In case of unexpected events requiring opioids or anaesthetics outside the protocol during the procedure, the patient will be withdrawn from the study.

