8.5 Replacement of individual subjects after withdrawal

In order to compete with possible dropouts, due to withdrawal for whatever reason or due to protocol violation, the sample size of the study is about 10% in excess of the results of the sample size calculation. In paediatric depth of anaesthesia studies dropout rates are usually within the range of +/- 5% and mostly due to equipment failure. As a consequence of secondary exclusion due to protocol violation or data registration failure, we choose to increase the number of subjects with 10% on beforehand. There is no need to replace individual subject after withdrawal.

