8.6 Follow-up of subjects withdrawn from treatment

Not applicable

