10. STATISTICAL ANALYSIS

10.1 Primary study parameter(s)

The time interval between the end of anaesthetic drug application and the moment when discharge criteria from the operating room are met (Steward score ≥ 3) is compared between the study groups. Therefore datasets will first be tested for normality by means of the Shapiro-Wilk normality test. As appropriate, either a Mann-Whitney-U-test or a t-test will be performed.

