10.3 Other study parameters

Descriptive statistics will be applied to demographic variables, continuous variables such as discharge times, incidence of recall of events during the procedure (awareness) and adverse events. All datasets will be tested for normality by means of the Shapiro-Wilk normality test.

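### Children are removed from the only primary analysis for events after randomisation, with no all-randomised analysis and no planned outcome follow-up, so the comparison can be biased in either direction

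*Combined protocol and SAP*

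**What the plan says.** Three rules take randomised children out of the comparison.

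- Section 5.3 counts any opioid or anaesthetic used outside the protocol as escape medication, and then: "The subject will be secondary excluded from analysis when escape medication is used".
- Section 8.4.1 covers unexpected events "requiring opioids or anaesthetics outside the protocol during the procedure, the patient will be withdrawn from the study".
- Section 4.3.2 lists protocol violation and "data registration failure" as secondary exclusion criteria, without defining either in the readable text.

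Section 8.5 budgets for these losses. It cites a usual dropout of about 5%, mostly from equipment failure, and then sets a 10% allowance: "As a consequence of secondary exclusion due to protocol violation or data registration failure". It plans no replacement. The entry for section 8.6, "Follow-up of subjects withdrawn from treatment", is not applicable.

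Section 10.1 compares the study groups on emergence time by a t-test or Mann-Whitney test, chosen after a normality check ("Therefore datasets will first be tested for normality by means of the Shapiro-Wilk normality test"). Section 10 gives no analysis set, missing-data rule or sensitivity analysis. CONSORT appears only in 11.2, in connection with eligibility and recruitment.

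Section 8.2 blinds the assessor, who enters when drug delivery stops. It states that the person giving anaesthesia cannot be blinded.

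**The concern.** Randomisation protects a comparison only while the children compared are those who were randomised. Here the reasons for removal arise afterwards, and some are tied to what the arms differ in. Sevoflurane adjusted to the DSA pattern is protocol treatment in one arm. In the other, moving away from 0.9 MAC or 2.3% end-tidal could be classed as a violation. Either arm could therefore lose more children, and an unblinded anaesthetist is involved in the events that trigger removal. Assessor blinding does not help, because intra-operative triggers come before the assessor enters.

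The loss may also be irreversible. A child withdrawn during the procedure leaves before emergence, so the time may never be recorded and no later all-randomised analysis could be built.

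The other endpoints are affected differently. Recall is descriptive (10.3: "incidence of recall of events during the procedure (awareness) and adverse events") and assessed only in children of at least 6 years, so the harm is missed events, not a biased test. Adverse events are recorded and followed under 9.2.1 and 9.4; what is lacking there is reporting by arm.

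**Working it through.** **1. The plan's own figures.** Inputs from 4.4: d = 0.6, Wilcoxon-Mann-Whitney test, power 0.90, alpha 0.05, equal groups. With asymptotic relative efficiency 3/π = 0.955 (normal parent), the effective size is n′ = n × 0.955, the noncentrality is d × √(n′/2), and df = 2n′ − 2. For n = 51: n′ = 48.7 and noncentrality = 0.6 × √24.35 = 2.96. Power is 0.902 one-sided, and 51 is the smallest n that reaches 0.90. The stated 51 is thus reproduced, but only one-sided; two-sided power at 51 is 0.834. The protocol does not state sidedness.

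Inflation: 51 × 1.10 = 56.1, stated as 56. The allowance is 56 − 51 = 5 per arm, and 5/56 = 8.9%.

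**2. Size of a possible bias.** The documents give no exclusion rate by arm and no link between exclusion and emergence time, so the counts below are assumptions. Model: no true effect, 56 per arm, normal emergence times, excluded children drawn at random from the slower half of their arm, two-sided Mann-Whitney at 0.05.

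The shift can be checked by hand. The slower half of a standard normal has mean √(2/π) = 0.798. Removing k of 56 children from it moves the arm mean by −k × 0.798/(56 − k):

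- k = 3: −2.394/53 = −0.045 SD
- k = 5: −3.990/51 = −0.078 SD
- k = 6: −4.788/50 = −0.096 SD

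Simulation (40,000 to 100,000 trials per row; Monte Carlo error about 0.1 percentage point):

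| Excluded, DSA v control | Type I error | Shift, DSA minus control (SD) |
|---|---|---|
| 0 v 0 | 4.9% | 0 |
| 3 v 0 | 5.4% | −0.045 |
| 3 v 1 | 4.9% | −0.03 |
| 3 v 3 | 4.7% | 0 |
| 5 v 0 | 6.6% | −0.079 |
| 5 v 3 | 5.0% | −0.03 |
| 6 v 0 | 7.4% to 7.6% | −0.094 |
| 6 v 1 | 6.7% | −0.08 |
| 6 v 6 | 4.4% | 0 |
| 1 v 6 | 6.7% | +0.08 |

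A negative shift flatters DSA. False positives in favour of DSA rise from 2.4% at 0 v 0 to 5.9% at 5 v 0 and 6.9% at 6 v 0. Relative to the planned effect, the shift is 0.079/0.6 = 13% at 5 v 0 and 0.094/0.6 = 16% at 6 v 0. The rejection rates do not depend on the normal shape; the SD shifts do.

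**3. A second mechanism.** Take 8 v 3 exclusions (11 of 112, close to the 10 budgeted) and a correlation of 0.5 between the reason for exclusion and emergence time (4,000 trials). Removing slow wakers shifts the difference by about −0.07 SD. Removing fast wakers shifts it by about +0.08 SD and, when the true effect is 0.6, lowers two-sided power from 0.87 to 0.75.

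**4. Power if everyone is kept.** With the effect unchanged at 0.6, two-sided power is 0.867 with 56 per arm against 0.834 with 51. Keeping everyone needs no extra patients.

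**The case against.** The best counter-argument is about size. Section 8.5 puts usual dropout near 5%, about 3 per arm, mostly from equipment failure, which has no shown link to arm. At 3 v 1 there is no inflation, and at 3 v 0 it reaches only 5.4%. Six exclusions (10.7%) exceed the plan's own allowance of five. This stands: at the usual dropout the effect is small, and it matters only when losses approach the allowance and are one-sided. But the 5% comes from other studies, and the protocol doubles it precisely because it expects secondary exclusions.

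A second argument is that the sponsor wanted "To exclude the impact of opioids on speed of recovery". That is a legitimate aim, and requiring caudal analgesia at entry does not guarantee that no opioid follows. But a need for extra drug after allocation may be a consequence of the strategy under test. The effect without escape drugs can be a supporting question; the plan does not name it as the target and gives no all-randomised analysis beside it.

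Third, the readable text may be incomplete: the flowchart cited in 8.3 is not shown and could name a population. Section 8.6 is also a template heading, and adverse events are followed under 9.4. So the claim that emergence times stop being collected is an inference from withdrawal during the procedure. None of this removes the explicit exclusion in 5.3.

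**Conclusion.** The concern holds. Followed as written, the protocol deletes randomised children from its only primary comparison for events that can depend on arm, and may leave no data with which to check the effect. Bias arises only if exclusions differ by arm and relate to emergence time. Under the illustrative assumptions it is negligible to small at 5% losses. It reaches about 0.08 SD, with type I error near 6.6%, if all five budgeted losses fall in one arm and come from its slower half. Direction cannot be determined from the documents. The case for correction rests on a bias in the primary result that could be neither measured nor undone afterwards, not on a large predicted number.

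**What to change.** Amend 4.3.2, 5.3, 8.4.1, 8.6 and 10 as follows.

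1. Make the primary analysis all randomised children in their assigned group, regardless of escape medication or protocol violation.
2. State that emergence time, recovery-room time, delirium, recall and adverse events continue to be collected in these children unless consent is withdrawn.
3. Let an EEG recording failure exclude a child only from the depth-of-hypnosis comparison.
4. Define protocol violation and data registration failure before the first patient.
5. Report escape-drug use, exclusions and missing emergence times by arm and reason, and state how missing emergence times are handled. An optional check, informative only if few are missing, ranks them slowest in one arm and fastest in the other, then reverses this.
6. Keep the current exclusion set as a per-protocol sensitivity analysis.

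The cost is protocol wording and a little continued data collection. The one downside is possible dilution of the effect estimate, which could offset the power gained from the larger analysed sample. Nothing changes in clinical management or in when escape medication is given.

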6. INVESTIGATIONAL PRODUCT

6.1 Name and description of investigational product(s)

Narcotrend™ monitor or Narcotrend compact M is an electroencephalographic monitor recording frontal EEG-activity. Multiple diagrams to interpret the EEG are available on this monitor. The extended version as used in the operating room in the Sophia Children's hospital offers a diversity of diagrams; the cerebrogram, the relative Band activities/Power, the Quantiles, the Power Spectrum, the Amplitude-Integrated EEG/Burst-Suppression-Ratio and Density Spectral Array.

6.2 Summary of findings from non-clinical studies

Not applicable

6.3 Summary of findings from clinical studies

The Narcotrend has been validated for use in children undergoing both surgical procedures under general anaesthesia and gastrointestinal endoscopy under procedural sedation in the Sophia Children's Hospital.¹⁹⁻²¹

6.4 Summary of known and potential risks and benefits

Not applicable

6.5 Description and justification of route of administration and dosage

Not applicable

6.6 Dosages, dosage modifications and method of administration

Not applicable

6.7 Preparation and labelling of Investigational Medicinal Product

Not applicable

6.8 Drug accountability

Not applicable

7. NON-INVESTIGATIONAL PRODUCT

Not applicable.

7.1 Name and description of non-investigational product(s)

Not applicable

7.2 Summary of findings from non-clinical studies

Not applicable

7.3 Summary of findings from clinical studies

Not applicable

7.4 Summary of known and potential risks and benefits

Not applicable

7.5 Description and justification of route of administration and dosage

Not applicable

7.6 Dosages, dosage modifications and method of administration

Not applicable

7.7 Preparation and labelling of Non Investigational Medicinal Product

Not applicable

7.8 Drug accountability

Not applicable

8. METHODS

8.1 Study parameters/endpoints

8.1.1 Main study parameter/endpoint

The primary endpoint of the study is the time interval between the termination of anaesthetic drug delivery and discharge from the operating theatre according to predefined discharge criteria.

8.1.2 Secondary study parameters/endpoints (if applicable)

Secondary end points are:

- Total time from discontinuation of anaesthetic drug delivery until discharge from the post anaesthesia care unit.
- The incidence of post-operative delirium
- Differences of depth of hypnosis during the procedure.
- Incidence of recall of events during the procedure (awareness)
- Adverse events

8.1.3 Other study parameters (if applicable)

Not applicable

8.2 Randomisation, blinding and treatment allocation

Patients will be allocated to either the intervention group or the control group by a computer-generated block randomisation. A paediatric anaesthetist who is not otherwise involved in this trial will perform the randomisation procedure, including the preparation of sealed envelopes with the randomisation codes per patient and the randomisation schedule.

The investigator who determines the hypnotic state of the patient after discontinuation of delivery of anaesthetic drugs is not present at the operating theatre during the surgical procedure. He enters the theatre at the moment of discontinuation of drug delivery, which equals the start of the emergence period. That enables us to blind the investigator as to the study-group assignment of the patient.

The member of the research team that provides general anaesthesia cannot be blinded with respect to group allocation. In patients allocated to the control group the screen of the Narcotrend monitor is obscured.

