Rationale:

Electroencephalographic density spectral array (DSA) is a three dimensional method to display electroencephalogram (EEG) signals consisting of the EEG frequency (y-axis), the power of the EEG signal (colour-coded to be integrated into a two dimensional plot) and the development of the EEG power spectrum over time (x-axis). DSA is routinely used to measure depth of hypnosis (DoH) by a part of the staff members in our department. When DSA is used, dose adjustments of sevoflurane will be made based on monitoring depth of anaesthesia. However, most of our colleague do not use DSA. Dose adjustment is then based on (subjective) clinical surrogate parameters, or in general mostly based on a minimal alveolar concentration of the anaesthetic gas that is used.

Electroencephalographic DSA monitoring provides continuous objective information on DoH and should result in a faster speed of emergence and recovery from general anaesthesia (GA). This will be addressed in a randomised controlled trial.

Objective:

To evaluate the influence of DSA monitoring, provided by the NarcotrendTM monitor, on the speed of emergence and recovery from GA.

Study design:

Single centre, prospective randomised, double-blind, controlled trial.

Study population:

Paediatric patients, aged \geq 6 months and \leq 12 years, scheduled for surgical procedure requiring general anaesthesia supplemented with caudal analgesia.

Intervention:

In patients randomised to the intervention group of the trial, the anaesthetic agent sevoflurane will be titrated according to the typical DSA pattern for GA with sevoflurane, provided by the NarcotrendTM.¹ In patients randomised to the control group, sevoflurane will be titrated according to a Minimal Alveolar Concentration (MAC) of 0.9 respectively an end tidal sevoflurane concentration of 2.3% based on standard practice in our paediatric anaesthesia department.

Main study parameters/endpoints:

The speed of emergence from GA (time interval from discontinuation of hypnotic agent until criteria for transfer from the operation theatre to the recovery room are met) is the primary

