3. STUDY DESIGN

Single centre, prospective, randomized, double blind trial.

In paediatric patients, aged 6 months until 12 years, scheduled for a surgical procedure which requires general anaesthesia supplemented with caudal analgesia. General anaesthesia is either guided by density spectral array or by a minimal alveolar sevoflurane concentration of 0.9 respectively an end tidal sevoflurane concentration of 2.3%.

The two study groups are compared with respect to the speed of recovery (primary objective). Secondary objectives of this trial are total time from discontinuation of anaesthetic drug delivery until discharge from the post anaesthesia care unit, the incidence of postoperative delirium, the difference in intra-operative blood pressure between the intervention group and the control group, differences of depth of hypnosis during the procedure, as measured by the Narcotrend monitorTM, the incidence of recall of events during the procedure (awareness) and adverse events.

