5. TREATMENT OF SUBJECTS

The effect of DSA on recovery of anaesthesia in children protocol

Standard anaesthesia monitoring is used during the procedure, ECG, pulse-oxymetry, capnometry and non-invasive measurement of blood-pressure.

Patients randomized to the control group are also attached to the Narcotrend monitor, but with the screen of the monitor obscured. The electroencephalographic data will later be compared to the data of the intervention group in order to assess for differences of depth of hypnosis during the procedure.

After complete recovery from GA, the day thereafter and two weeks later, parents or legal guardians will be contacted via telephone for a systematic interview with the patient if aged > 6 years. This systematic interview is the “Modified Brice-interview”, which is the golden standard for the detection of recall of intraoperative events.^{17,18} Brice interviews will only be performed in patients of at least 6 years of age, because it is known that interviews taken in children of younger ages are likely not to provide the interviewer with reliable information. At the end of the procedure, sevoflurane will be stopped and washed out with 10L flow, FiO₂ 0.5. The patients will be otherwise left undisturbed on the operation table. The sound level in the operation theatre will be reduced to a minimum.

The speed of emergence and recovery will be assessed with the Steward Recovery Score from Anaesthesia.¹³

The incidence of postoperative delirium will be assessed with the Cornell Assessment of Postoperative Delirium (CAPD).^{14,15}

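### Section 8.2 keeps the assessor out until sevoflurane stops but describes no shielding of agent readings, and obscures the Narcotrend screen only in controls, so cues to the arm may remain when he starts timing the primary endpoint

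*Combined protocol and SAP*

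**What the plan says.** Section 8.2 describes the assessor's absence during surgery: "The investigator who determines the hypnotic state of the patient after discontinuation of delivery of anaesthetic drugs is not present at the operating theatre during" [surgery]. It then gives his time of entry: "He enters the theatre at the moment of discontinuation of drug delivery, which equals the start of the emergence period". From this it concludes: "That enables us to blind the investigator as to the study-group assignment of the patient". No other measure to blind him is described.

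The same section says that the person giving the anaesthetic "cannot be blinded with respect to group allocation". The only display masking in the plan is the Narcotrend screen, obscured in control patients (sections 5 and 8.2). Nothing is said about an agent reading, the vaporiser, the anaesthetic record, or the Narcotrend screen in the intervention arm.

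The arms differ in how sevoflurane is guided. For controls, the Summary says "sevoflurane will be titrated according to a Minimal Alveolar Concentration (MAC) of 0.9 respectively an end tidal sevoflurane concentration of 2.3" per cent. For the intervention arm, "the anaesthetic agent sevoflurane will be titrated according to the typical DSA pattern for GA with sevoflurane". Section 5 describes the end of the case: "At the end of the procedure, sevoflurane will be stopped and washed out with 10L flow".

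The primary endpoint (sections 2 and 10.1) runs from the end of drug delivery to a Steward score of at least 3. Section 3 labels the design: "Single centre, prospective, randomized, double blind trial". The Summary uses the same label.

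**The concern.** The assessor is the one safeguard against detection bias, because the anaesthetist knows the arm. The primary time ends when an observer judges that the child responds to stimuli, keeps a good airway and moves (section 1.5.1). Those are judgements, and the team states that it expects faster recovery with DSA (sections 1.6 and 13.2). If the assessor can form a view of the arm when he walks in, any unconscious lean would probably favour the hypothesis.

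Keeping him out during surgery removes what happened earlier. It does not remove what the equipment still shows at the moment of entry. Two cues could remain. One is the agent reading, which bears on the very thing that separates the arms. The other is the state of the Narcotrend screen, which by the plan is covered in one arm only. Bias from either could not be separated from a treatment effect after recruitment.

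**Working it through.** **Does the timing remove the information?**

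- Entry coincides with discontinuation (8.2), and washout starts at discontinuation (section 5). At entry, therefore, the end-tidal value has not yet fallen far from its maintenance level.
- Controls are titrated to MAC 0.9 / end-tidal 2.3%; the DSA arm has no fixed concentration (Summary, section 3). A reading near 2.3% makes control more likely, and one well away from it makes DSA more likely.
- Section 5 lists ECG, pulse oximetry, capnometry and blood pressure, and names no agent analyser. A control arm defined by an end-tidal sevoflurane value nevertheless needs such a reading in theatre. Whether the assessor can see it is not stated.
- For the Narcotrend screen no inference about dose is needed. If it is in view, obscured means control.

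**How informative could one agent reading be?**

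The documents give no spread of end-tidal values and no DSA-arm mean, so these inputs are assumptions: control readings normal with mean 2.3% and SD 0.1 to 0.3; DSA readings normal with mean 1.8% to 2.1% and SD 0.3. With equal allocation, the best possible guess is right with probability

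a = 0.5 × ∫ max(f_control, f_DSA) dx.

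| Control SD | DSA mean 2.1% | DSA mean 2.0% | DSA mean 1.8% |
|---|---|---|---|
| 0.1 | 78% | 83% | 91% |
| 0.2 | 67% | 74% | 85% |
| 0.3 | 63% | 69% | 80% |

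Chance is 50%. The control SD matters as much as the dose difference: with both means at 2.3%, the result is 74% at control SD 0.1, 60% at 0.2 and 50% at 0.3, where the two distributions coincide.

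**What would that do to the primary test?**

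Section 4.4 gives 51 analysed children per group. That figure reproduces as a one-sided Wilcoxon-Mann-Whitney calculation at alpha 0.05 with d = 0.6 (power 0.902). Section 4.4 does not state sidedness; I use a two-sided 5% test below.

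Suppose that DSA has no true effect, and that a child believed to be in the DSA arm is scored faster by s SD than one believed to be a control. The share believed to be DSA differs between arms by sensitivity + specificity − 1 = 2a − 1. The bias in the comparison is therefore s(2a − 1), and the noncentrality is

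δ = s(2a − 1) × √(51/2) = s(2a − 1) × 5.05.

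Type I error = Φ(δ − 1.96) + Φ(−δ − 1.96).

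| | s = 0.1 | s = 0.2 |
|---|---|---|
| a = 0.631 (2a − 1 = 0.261) | δ = 0.13, 5.2% | δ = 0.26, 5.8% |
| a = 0.912 (2a − 1 = 0.824) | δ = 0.42, 7.0% | δ = 0.83, 13.2% |
| a = 1 (perfect unblinding) | δ = 0.50, 8.0% | δ = 1.01, 17.3% |

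Allowing for the efficiency of the rank test lowers the last row slightly, to 7.8% and 16.4%. For scale, a shift of 0.2 SD is one third of the planned effect (0.2/0.6 = 0.33).

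**The case against.** The best reply is that the plan nowhere places an agent display, a trend screen or a vaporiser dial in the assessor's line of sight. The end-tidal target implies that the anaesthetist has a reading, not that the assessor sees it. Washout at high flow also makes the current value uninformative soon after entry, unless a trend or record preserves it. This stands. The point is therefore that shielding is not described, not that the assessor is unblinded.

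A reader might also infer that controls sit at a steady 2.3%, so that one glance settles the arm. The documents do not support this. The control concentration is titrated towards a target. Section 1.4 says that concentration is adjusted to age and clinical status and that MAC falls with age; sections 5.1 and 13.2 add clinical parameters or signs to the comparator. Control values may vary considerably, and a DSA child may be near 2.3%. The cue is probabilistic.

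A third objection is that the Narcotrend screen is the plainer leak and that, while it stands, the gas reading adds little. That is fair on priority. Covering the screen in both arms would still leave the gas reading open, however, so one paragraph should close both.

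Finally, the double-blind label misleads nobody who reads 8.2, which says plainly who is not blinded. I agree that this is a matter of wording and changes no analysis.

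**Conclusion.** The concern holds as a gap in the described safeguards. Entry at discontinuation does not by itself blind the assessor, because the agent reading is then still near its maintenance level and the arms are titrated to different guides. Obscuring the Narcotrend screen only in controls adds a more direct cue if it is visible.

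On the stated assumptions, one agent reading gives the right arm in about 63% to 91% of children. The resulting two-sided type I error is about 5% to 7% for a 0.1 SD scoring shift and 6% to 13% for 0.2 SD. A reader might take 8% and 17% as the expected inflation. Those are ceilings that require every child to be classified correctly, which an agent reading would not achieve under these assumptions; a visible Narcotrend screen could come close.

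The reading spreads, the DSA mean and the size of the scoring shift are all illustrative. The mechanism follows from the plan's own timing and titration rules plus one inference, that an agent reading is present in theatre. The documents do not show that the assessor sees it, or that bias will occur. The change is worth making because it is cheap now and the bias could not be corrected later.

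**What to change.** Add a paragraph to section 8.2, applying to both arms. Before the assessor enters:

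- the agent and MAC values, any trend display, the vaporiser setting and the Narcotrend screen are placed out of his view, while the anaesthetist keeps whatever view the protocol allows;
- staff do not discuss the arm or the sevoflurane dose in his presence;
- the anaesthetic record is withheld from him until Steward scoring is complete.

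As a secondary wording change, replace double blind with assessor-blinded in the Summary and section 3, so that they agree with 8.2.

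The cost is protocol text, a shield or turned screen, and one extra set-up step per case. The treatment, endpoint, analysis and sample size do not change.

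### The Narcotrend screen is obscured in controls only, so its state could reveal the arm to the assessor who enters as sevoflurane is stopped

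*Combined protocol and SAP*

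**What the plan says.** Section 8.2 deals with the two roles separately. On the anaesthesia provider: "The member of the research team that provides general anaesthesia cannot be blinded with respect to group allocation". The sentence on the screen follows directly: "In patients allocated to the control group the screen of the Narcotrend monitor is obscured". On the assessor, the section keeps him out of theatre during surgery and then says: "He enters the theatre at the moment of discontinuation of drug delivery, which equals the start of the emergence period". From this it concludes: "That enables us to blind the investigator as to the study-group assignment of the patient".

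Section 5 repeats the screen rule: "Patients randomized to the control group are also attached to the Narcotrend monitor, but with the screen of the monitor obscured". It then explains why controls are monitored at all: "The electroencephalographic data will later be compared to the data of the intervention group". For the end of the case it says: "At the end of the procedure, sevoflurane will be stopped and washed out with 10L flow", and then: "The patients will be otherwise left undisturbed on the operation table". Noise in theatre is also to be kept low. These steps are given without distinction by group, and none of them mentions the monitor.

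The Summary (Intervention) has sevoflurane titrated to the DSA pattern on this monitor in the intervention group, and to a MAC or end-tidal value in controls. Section 8.3 contains only a reference to a flowchart, which is not shown in our copy.

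**The concern.** Keeping the assessor out of theatre removes what he might have seen earlier. It does nothing about what is in front of him when he walks in. The text fixes the state of the screen in one arm only, and he arrives just as the two arms' screens have been in opposite states.

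The primary endpoint (sections 8.1.1 and 10.1) is the time from the end of drug delivery until the operating-room criteria are met. Section 3 calls the trial double blind, but the provider knows the arm, so protection of this endpoint rests largely on the assessor. If he can infer the arm, detection bias in the primary comparison becomes possible. Section 1.5.1 asks for a response to stimuli, and the text does not say which stimulus is used or how often it is tried, so some of the judgement is left to the observer.

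**Working it through.** No figure in the plan bears on this point and there is nothing to recalculate. The check is to set the passages side by side and follow the screen through the case.

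| Stage | Control group | DSA group |
|---|---|---|
| During surgery | Screen obscured (sections 5 and 8.2) | Screen must be legible, because titration uses it (Summary, Intervention) |
| Sevoflurane stopped, assessor enters (section 8.2) | No change stated | Not described |
| Emergence, criteria judged | No change stated | Not described |

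1. **Is the difference between arms created by the plan itself?** Yes, up to the moment sevoflurane is stopped. One arm is covered by an explicit rule. The other must be uncovered for the intervention to work.
2. **Does any text we can read remove the difference before the assessor can see the screen?** No. The end-of-case steps in section 5 cover wash-out, leaving the patient undisturbed and noise. Section 8.2 covers only his absence and the time of his entry. Neither says that the display is covered, turned away or switched off in both groups, or that the provider must not disclose the arm.
3. **Does the assessor's judgement feed the primary endpoint?** Section 8.2 says he judges the patient's hypnotic state once drug delivery has stopped, and sections 1.5.1 and 10.1 make the endpoint depend on Steward criteria. That he also records the time is a fair inference, but it is not stated.
4. **What else must hold for harm to follow?** The DSA screen would have to stay uncovered after sevoflurane is stopped, the monitor would have to be in his view, he would have to connect its state with the arm, and that knowledge would have to move his rating. The documents neither state nor exclude any of these.

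The text therefore establishes an arm-specific difference at the time of entry and no stated step that removes it. It does not establish that unblinding occurs.

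**The case against.** The strongest objection is that the study procedures sit in a flowchart we cannot see. Content lost in that way cannot be counted as missing from the plan, and an end-of-surgery sequence is just what such a chart could hold. This stands, and it limits the point to what the text says.

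Second, the screen rule may not concern the assessor at all. Its position in section 8.2, right after the sentence on the provider, and in section 5, beside the later EEG comparison, fits a rule meant to stop the provider from using the EEG in controls. That is plausible. The purpose of the rule does not change its side effect, though: a screen covered in one arm only is a cue whatever the reason for covering it.

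Third, the scope for bias is limited. The threshold is a score of at least 1 in each Steward domain, and wash-out and handling are described alike for both groups. This also stands, but it reduces the scope without removing it. The unspecified stimulus would be a gap in the endpoint definition even under perfect blinding. Here it matters only because it leaves room for judgement.

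A reader might go further and infer that the assessor is in fact unblinded, or that the primary result will favour DSA because the authors expect faster recovery with it (Summary and sections 1.6 and 13.2). The documents support neither. They do not place the monitor in his view, and the authors' expectation says nothing about how this observer would rate. One could also assume a shift in timing and compute an inflated false-positive rate, but nothing in the plan supplies such a shift.

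**Conclusion.** The point holds as a possible cue, not as demonstrated unblinding. The text obscures the screen in controls only, requires it to be legible in the DSA group until sevoflurane is stopped, brings the assessor in at that moment, and rests his blinding on his earlier absence alone. If the screen is in his view, its state could reveal the arm while he judges the operating-room criteria.

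The size and direction of any bias are unknown and no number is offered. Equal allocation (56 per group, section 4.4) says how many patients fall under each screen state. It does not measure bias. The conclusion assumes that the flowchart contains no masking step and that the DSA display is left as it was for titration. If either assumption fails, what remains is to say so in the text. The change is worth making because the difference comes from the plan's own rule, the endpoint is observer-rated, and the remedy costs almost nothing. Confidence is moderate.

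**What to change.** Add to sections 5 and 8.2:

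> In both groups the Narcotrend display is positioned so that it cannot be seen by a person entering the theatre, or is covered in the same way in both groups as sevoflurane is stopped and before the assessor comes within view of it; EEG recording continues. The anaesthesia team does not disclose the arm until the operating-room criteria have been met and recorded.

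The two options deal with the timing. Section 8.2 has the assessor enter at the moment of discontinuation, so an instruction simply to cover the screen before he enters would either cut into titration or delay his entry past the start of the primary interval. Positioning the display avoids the conflict. Covering it as the drug is stopped, before he can see it, resolves it. If the flowchart already contains such a step, repeat it in the text.

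The cost is one small step per case, 56 + 56 = 112 planned cases, with no added staff or equipment and no change to sample size or analysis.

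The change removes the Narcotrend cue only. Controls are held to a MAC or end-tidal sevoflurane value, and the documents do not say whether that reading is in the assessor's view. The authors should state this as well.
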